11.4 Statistical analysis of the population

- Analysis of outcome measures: analysis of the population who have completed the corresponding data collection;;
- 2 Safety evaluation: included in the analysis as long as he/her had received one session of intervention.

11.5 Statistical analysis method

Data will be preprocessed and/or analyzed using SPSS25.0, SAS9.2, Matlab, and R.

• Analysis of the primary outcome measures:

SRS scores at baseline, immediately after the end of 5-day intervention and 4 weeks after the end of 5-day intervention will be analyzed using repeated measures ANOVA.

2 Analysis of other behavioral outcome measures:

RBS-R, BRIEF, PSQ scores at baseline, immediately after the end of 5-day intervention, and 4 weeks after the end of 5-day intervention will be analyzed using repeated measures ANOVA or Friedman test.

CARS, PPVT, CCDI, MAIN scores at baseline and 4 weeks after the end of 5-day intervention will be analyzed using paired-samples t-tests or Mann-Whitney Wilcoxon test.

3 EEG analysis

EEG data will be preprocessed and analysed by MATLAB. Changes in the electrophysiologicalactivity characteristics of the brain at baseline, immediately after the end of 5-day intervention and 4 weeks after the end of 5-day intervention will be analyzed and then correlated with clinical behavioral outcome.

4 Safety evaluation

Summarize the occurrence of adverse events: summarize the number of cases,

Efficacy and mechanistic of repeated transcranial magnetic stimulation in children with autism spectrum disorder: an open-label clinical trial. NCT05472870

Version: 2.0/April 2, 2022

instances, and incidence of adverse events and list all adverse events, those related to the study intervention protocol, serious adverse events, and those leading to exit; list the number of cases, instances, and incidence of mild, moderate, and serious adverse events; give a description for adverse events related to the intervention.

SAnalysis of baseline characteristics

The analysis of baseline characteristics included: demographics (age and gender); baseline analysis of each observation used in this study.

The number of cases, mean, standard deviation, median, minimum and maximum values were calculated when the variables were quantitative indicators; the number of cases and composition ratio were calculated when the variables were categorical indicators.

12. 0 Principal Investigator and contact person

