8.2 Adverse events and incidence

A semi-structured interview was administered following each treatment session and follow-up by the rTMS technician. A standardized adverse events assessment form was completed if adverse events or physical discomfort were reported. Using this form, detailed descriptions of the adverse events experienced were recorded, including rating the event as mild (no impairment, no need stopping trial), moderate (some impairment, need stopping trial, no need for intervention), severe (evidence of impairment, need stopping trial and need for intervention).

9. 0 Adverse events and serious adverse events

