9.2 Record of adverse events

Record all adverse events that occurred after signing the informed consent form. The contents of each adverse event record should include the following points:

- Duration of the adverse event : start time and end time;
- **2**Severity of adverse events:

Mild-no impairment, no need stopping trial Moderate-some impairment, need stopping trial, no need for intervention Severe-evidence of impairment, need stopping trial and need for intervention;

• Relationship between adverse events and intervention: Investigators assessed the correlation between adverse events and the intervention as: positive / likely related

/ possibly related / likely unrelated / unrelated;

4 Management of adverse events: The investigator should follow up the adverse events until the symptoms disappear or stabilize; if the adverse event remains at the end of the study, follow up again within one month after the end of the study.

The intervention used in this study is rTMS, in principle, there is no safety risk in the use of rTMS in children if the safety guidelines developed by the international expert panel are strictly adhered to. However, rTMS may bring temporary minor discomfort such as scalp discomfort, localized pain, dizziness, headache, fatigue, tinnitus, anxiety, etc., mostly relieved within 24 hours. Serious side effects of seizures and neurocardiogenic syncope induced during stimulation have also been reported, but subjects who experienced these two adverse reactions had a history of depression and/or syncope.

The intervention process of this study is conducted in the hospital, and the subjects will be closely followed and supported in case of adverse reactions; if medical treatment is needed, the pediatrician will provide the treatment plan and follow-up visits. In addition, the study will continue to follow up the adverse events within 4 weeks after the 5-day intervention.

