9.3. Serious Adverse Events

Serious adverse events (SAE) are clinical medical events that occur during the course of the study that result in death or life-threatening, require hospitalization or prolonged hospitalization, and cause disability or dysfunctional impairment.

If a serious adverse event occurs during the study, whether related to the intervention, appropriate treatment measures must be taken immediately and reported to the principal investigator and the ethics committee within 24 hours.

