10.0 Ethics committee and informed consent form

10.1 Ethics committee

Prior to the start of the study, the protocol and informed consent should be reviewed and approved by the ethics committees of the study centers. During the study, any change of the study protocol to the Ethics Committee shall be filed with the Ethics Committee; in case of serious adverse event, the Ethics Committee shall be notified within 24 hours.

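### Does the safety summary in section 11.5 lose the severe grade by printing serious in its place?

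*Combined protocol and SAP*

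**What the plan says.** Three parts of the combined protocol and SAP bear on this point.

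- **Severity grade.** Section 8.2 has a three-step scale on the adverse event form, whose top step is "severe (evidence of impairment, need stopping trial and need for intervention". Section 9.2 repeats the scale for the event record: the top grade is "Severe-evidence of impairment, need stopping trial and need for intervention" and the one below it is "Moderate-some impairment, need stopping trial, no need for intervention".
- **Seriousness.** Section 9.3 defines a serious adverse event by what it leads to: events that "result in death or life-threatening, require hospitalization or prolonged hospitalization, and cause disability or dysfunctional impairment". A reporting duty attaches to this class and not to the grade. Section 10.1 states that "in case of serious adverse event, the Ethics Committee shall be notified within 24 hours", and section 9.3 sets the same time limit.
- **Planned summary.** The safety paragraph of section 11.5 asks for a list of all adverse events, "those related to the study intervention protocol, serious adverse events, and those leading to exit". Later in the same sentence it asks for numbers of cases, instances and "incidence of mild, moderate, and serious adverse events".

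The word *severe* does not occur in section 11.5. Section 11.4 takes as the safety population every child who received at least one session.

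**The concern.** Severity and seriousness are different classifications in this protocol. The first describes intensity and what had to be done about the event; the second describes its outcome and starts a 24-hour clock. The breakdown in section 11.5 begins on the first scale and ends on a word that belongs to the second.

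Taken literally, this leaves a gap. A child may need medical treatment without being admitted to hospital; section 9.2 allows for this, since "if medical treatment is needed, the pediatrician will provide the treatment plan and follow-up visits". Such an event could be graded severe without being serious, and it would then be neither mild, nor moderate, nor serious. This clause is the only place where section 11.5 plans incidence by grade, so the highest grade would have none. In an open-label trial of an accelerated, high-dose stimulation course in children, with safety among its aims (section 1.0), that would be an awkward omission: the third category could read zero although a severe event had occurred.

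**Working it through.** The plan gives no event rate, and no figure depends on this clause. The check is therefore a comparison of categories, followed by a check of whether the severe grade can be recovered from the other planned outputs.

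**1. Recorded against summarized categories**

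- Recorded (8.2, 9.2): mild, moderate, severe.
- Summarized (11.5): mild, moderate, serious.

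| Event | Categories it enters if *serious* is literal | Categories it enters if *severe* is meant |
|---|---|---|
| Mild or moderate, not serious | one | one |
| Severe, not serious | none | one |
| Severe and serious | one | one, plus the separate list of serious events |
| Mild or moderate, and serious (if it can occur) | two | one, plus the separate list of serious events |

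The literal reading leaves one kind of event out and could count another twice. The other reading places every event exactly once.

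**2. Which reading the text supports**

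- Serious events already have their own item earlier in the sentence. Under the literal reading the breakdown would repeat that item and drop a recorded grade.
- The word stands third after *mild* and *moderate*, where the recorded scale has *severe*.
- The protocol also uses *serious* loosely, as a word of degree. Exclusion criterion F in section 4.4 applies it to heart disease and uses *severe* for hearing loss in the same line. Section 9.2 applies it to side effects such as seizures.
- Whoever tabulates the severity field will find three values in it, the third being severe.

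**3. Whether the severe grade can be recovered under the literal reading**

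*By subtraction.* Take three children: A has one mild and one severe event, B one moderate, C one mild.

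- Instances: 4 in all − 2 mild − 1 moderate = 1 severe, which is correct.
- Children: 3 with any event − 2 with a mild event (A, C) − 1 with a moderate event (B) = 0 severe, but the true number is 1 (A).

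Subtraction thus gives the events but not the children, because one child can have events of more than one grade over 10 × 5 = 50 sessions (section 5.1).

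*By direct count.* Section 9.2 requires a severity grade in each event record, and section 11.5 lists all events. Counting the children with at least one event graded severe gives 1 (child A), which is correct. This needs no new data.

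*From events leading to exit.* This count is not a substitute, because moderate and severe events both carry the need to stop and would be pooled in it.

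The direct count is enough. In a trial planned for at least 30 children (section 4.2) it is a short task.

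**4. What depends on the word**

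The grade is recorded whatever section 11.5 says. The 24-hour notice depends on section 9.3 and is unaffected. The efficacy analyses, the sample size and the safety population do not use the clause.

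**The case for a change.** The strongest case for a change is that the two terms are not synonyms here. The protocol defines them separately, ties a reporting duty to only one of them, and uses *serious adverse events* in the defined sense earlier in the same sentence; a careful programmer could fairly give the word the same meaning again. Nothing elsewhere equates the terms. The other planned counts do not isolate the severe grade, and subtraction fails for children. Safety is among the trial's aims, and the correction would cost one word.

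Most of this is right as a description of the text. The mismatch is genuine, a severe event that is not serious is possible under the protocol's own wording, and subtraction does fail.

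The step from mismatch to harm does not hold. It needs a reading that makes the sentence repeat itself and ignore a grade the trial records, and it needs an analyst to stop at that line although the listing shows the event. The size of the gap is also uncertain. Section 9.3 includes impairment of function among its outcomes, while both upper grades mention impairment, and the protocol does not draw the boundary. Events that are severe but not serious may be fewer than the concern supposes.

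A confidence interval for an assumed one, two or three affected children among 30 would not help. It would describe sampling uncertainty for any event in a trial of that size and would be the same with the wording corrected.

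**Conclusion.** No change to the plan follows. Section 11.5 very probably prints *serious* where *severe* was meant, and readers may take it that way. This is an inference from the sentence and the recorded scale, since the documents do not state it. It is a clerical slip and not a choice of analysis.

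In size, the slip affects one label in a descriptive safety summary. At worst, if the label is followed literally, a severe event that is not serious is missing from one line of the report while remaining in the full listing, where the children concerned can be counted. No efficacy result, sample size, error rate, data collection or reporting duty moves, and the safety conclusion should be the same.

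This rests on two assumptions: that the severity grade is completed for each event as section 9.2 requires, and that the listing in section 11.5 is drawn from those records. If the grade were not recorded, severe events could not be counted under either wording; that would be a failure of data collection which changing the word would not repair.
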